#### 4.2.2. Exclusion Criteria

A subject will not be eligible for inclusion in this study if any of the following criteria apply:

1. B-cell Therapy: Have received treatment with any B cell targeted therapy (e.g., rituximab, other anti-CD20 agents, anti-CD22 [epratuzumab], anti-CD52 [alemtuzumab], BlyS-receptor fusion protein [BR3], Transmembrane activator and calcium-modulator and cytophilin ligand interactor [TACI] Fc, or belimumab) at any time.
2. The subject has received a biologic investigational or non-investigational agent within 12 months prior to Day 0.
3. Received intravenous immunoglobulin (IVIG), plasmapheresis, hemodialysis, intravenous cyclophosphamide, or high dose prednisone and its equivalents (>60mg/day) within 6 months prior to Day 0.
4. The subject has received a non-biologic investigational agent within 2 months prior to Day 0.
5. The subject is currently participating in another clinical study or post-marketing study in which the subject is or will be exposed to an investigational agent.
6. The subject has severe lupus kidney disease (defined by proteinuria >6g/24h) within 6 months prior to the Screening visit.
7. History of a major organ transplant (eg. heart, lung, renal, liver) or hematopoietic stem cell/marrow transplant.
8. Active CNS lupus [including seizures, psychosis, organic brain syndrome, cerebrovascular accident (CVA), motor neuropathy, vasculitis] requiring medical intervention within 6 months prior to Screening visit.
9. **Infections:** Have required management of acute or chronic infections, as follows:
  - Currently on any suppressive therapy for a chronic infection (such as tuberculosis, pneumocystis, cytomegalovirus, herpes simplex virus, herpes zoster and atypical mycobacteria).
  - Hospitalisation for treatment of infection within 2 months prior to Day 0.

- Use of parenteral (IV or intramuscular [IM]) antibiotics (antibacterials, antivirals, anti-fungals, or anti parasitic agents) within 2 months prior to Day 0.
10. The subject has-IgA deficiency (IgA level <10 mg/Dl).
  11. Have a history of an anaphylactic reaction to parenteral administration of contrast agents, human or murine proteins or monoclonal antibodies.
  12. Uncontrolled other diseases: History or clinical evidence of active significant acute or chronic diseases (i.e., cardiovascular, pulmonary, untreated hypertension, anemia, gastrointestinal, hepatic, renal, neurological, cancer, or infectious diseases) which, in the opinion of the investigator, could confound the results of the study or put the subject at undue risk.
  13. Have a planned surgical procedure, or a history of any other medical disease, or laboratory abnormalities, or conditions which would make the subject (in the opinion of the Investigator) unsuitable for the study.
  14. The subject has an abnormality on 12-lead ECG at screening which is clinically significant in the opinion of the investigator, and which could confound the results of the study. Inclusion may put the subject at undue risk.
  15. Have evidence of current drug or alcohol abuse or dependence.
  16. Aspartate aminotransferase (AST) and alanine aminotransferase (ALT)  $\geq 2x$  upper limit of normal (ULN); alkaline phosphatase and bilirubin  $>1.5xULN$  (isolated bilirubin  $>1.5ULN$  is acceptable if bilirubin is fractionated and direct bilirubin  $<35\%$ ).
  17. Have a historically positive human immunodeficiency virus (HIV) test or test positive at screening for HIV.
  18. History of or positive test at screening visit for any of Hepatitis B surface antigen (HbsAg), anti- Hepatitis B core antibody (HbcAb) or anti-hepatitis C virus antibodies (HCVAb). If only anti-HbcAb result is positive, HBV-DNA test will be performed. If hepatitis B virus (HBV)-DNA results in negative, the patient is eligible.

NOTE: For those subjects included, additional ongoing assessment is required (see Section [6.2.1.1](#)).

19. **Laboratory Abnormalities:** Have a Grade 3 or greater laboratory abnormality based on the protocol toxicity scale [[Appendix 3](#)] except for the following that are allowed:
  - Stable Grade 3 prothrombin time (PT) secondary to warfarin treatment.

- Stable Grade 3/4 proteinuria ( $\leq 6$  g/24 hour equivalent by spot urine protein to creatinine ratio allowed).
  - Stable Grade 3 hypoalbuminemia due to lupus nephritis, and not related to liver disease or malnutrition.
  - Stable Grade 3 neutropenia or stable Grade 3 white blood cell count.
20. Subjects who have evidence of serious suicide risk including any history of suicidal behavior in the last 6 months or who, in the investigator's opinion, pose a significant suicide risk.
21. Received a live vaccine within 30 days of baseline (Day 0).
22. Have a history of malignant neoplasm within the last 5 years, except for adequately treated cancers of the skin (basal or squamous cell) or carcinoma in situ of the uterine cervix.

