##### 5.2.1. Liver Chemistry Stopping Criteria

Liver chemistry threshold stopping criteria have been designed to assure subject safety and to evaluate liver event etiology (in alignment with the FDA premarketing clinical liver safety guidance).

Study treatment will be stopped **for a subject** if the following liver chemistry stopping criteria is met:

- ALT  $\geq 3 \times$ ULN

NOTE: Refer to [Appendix 1](#) for details of the required assessments if a subject meets the above criteria.

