- Subjects with ALT  $\geq 3 \times \text{ULN}$  **but**  $< 5 \times \text{ULN}$  **and** bilirubin  $< 2 \times \text{ULN}$ , without hepatitis symptoms or rash, and who can be monitored weekly for 4 weeks
- Notify the GSK medical monitor within 24 hours of learning of the abnormality to discuss subject safety.
- Must return weekly for repeat liver chemistries (ALT, AST, alkaline phosphatase, bilirubin) until they resolve, stabilize or return to within baseline
- If at any time these subjects meet the liver chemistry stopping criteria, proceed as described above
- If, after 4 weeks of monitoring, ALT  $< 3 \times \text{ULN}$  and bilirubin  $< 2 \times \text{ULN}$ , monitor subjects twice monthly until liver chemistries normalize or return to within baseline values.

For criteria 1-3, make every attempt to carry out the **liver event follow up assessments** described below:

- Viral hepatitis serology including:
  - Hepatitis A IgM antibody;
  - Hepatitis B surface antigen and Hepatitis B Core Antibody (IgM);
  - Hepatitis C ribonucleic acid (RNA);
  - Cytomegalovirus IgM antibody;
  - Epstein-Barr viral capsid antigen IgM antibody (or if unavailable, obtain heterophile antibody or monospot testing);
  - Hepatitis E IgM antibody
- Blood sample for pharmacokinetic (PK) analysis, obtained within one to two weeks after the liver event. Record the date/time of the PK blood sample draw and the date/time of the last dose of IP prior to blood sample draw on the CRF. If the date or time of the last dose is unclear, provide the subject's best approximation. If the date/time of the last dose cannot be approximated OR a PK sample cannot be collected in the time period indicated above, do not obtain a PK sample. Instructions for sample handling and shipping are in the SPM.
- Serum creatine phosphokinase (CPK) and lactate dehydrogenase (LDH).
- Fractionate bilirubin, if total bilirubin  $\geq 2xULN$
- Obtain complete blood count with differential to assess eosinophilia
- Record the appearance or worsening of clinical symptoms of hepatitis, or hypersensitivity, such as fatigue, nausea, vomiting, right upper quadrant pain or tenderness, fever rash or eosinophilia as relevant on the AE report form
- Record use of concomitant medications, acetaminophen, herbal remedies, other over the counter medications, or putative hepatotoxins, on the concomitant medications report form.
- Record alcohol use on the liver event alcohol intake case report form

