## 12. APPENDICES

### 12.1. Appendix 1: Liver Safety Process

The procedures listed below are to be followed if a subject meets the liver chemistry stopping criteria defined in Section 5.2.1:

- Notify the GSK medical monitor within 24 hours of learning of the abnormality to confirm the subject's study treatment cessation and follow-up.
- Complete the "Safety Follow-Up Procedures" listed below.
- Complete the liver event case report forms. If the event also meets the criteria of an SAE (see Section 7.1.3), the SAE data collection tool will be completed separately with the relevant details.
- Upon completion of the safety follow-up withdraw the subject from the study unless further safety follow up is required
- Do not restart study treatment
- Refer to the Flow chart for a visual presentation of the procedures listed below.

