**12.3 Appendix 3: Adverse Event and Laboratory Value Severity Grade Tables (continued)**

CHEMISTRIES (continued)	GRADE 1 MILD	GRADE 2 MODERATE	GRADE 3 SEVERE	GRADE 4 POTENTIALLY LIFE-THREATENING
Uric Acid				
Hyperuricemia	7.5-10.0 mg/Dl	10.1-12.0 mg/Dl	12.1-15.0 mg/Dl	>15.0 mg/Dl
Liver Transferases (AST, ALT, and GGT)	1.25-2.5 x ULN	>2.5-5.0 x ULN	>5.0-10.0 x ULN	>10.0 x ULN
Alkaline Phosphatase	1.25-2.5 x ULN	>2.5-5.0 x ULN	>5.0-10.0 x ULN	>10.0 x ULN
Pancreatic Enzymes				
Amylase	>1.0-1.5 x ULN	>1.5-2.0 x ULN	>2.0-5.0 x ULN	>5.0 x ULN
Pancreatic amylase	>1.0-1.5 x ULN	>1.5-2.0 x ULN	>2.0-5.0 x ULN	>5.0 x ULN
Lipase	>1.0-1.5 x ULN	>1.5-2.0 x ULN	>2.0-5.0 x ULN	>5.0 x ULN
Hypoglobulinemia (IgG)*	550-700 mg/Dl	400-549 mg/Dl	250-399 mg/Dl	<250 mg/Dl
				(continued)

\*[Eibl, 1995; Goldfarb, 2001; Yamini, 2001].

Modified from DMID Adult Toxicity Tables, 2001

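### Exclusion 16 does not say whether its liver limits apply singly or jointly; read literally it admits an isolated ALT of 2.0 to 5.0 × ULN, part of which already meets the Section 5.2.1 stopping criterion

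*Protocol*

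**What the plan says.** **Eligibility.** Protocol Section 4.2.2 opens its list with "A subject will not be eligible for inclusion in this study if any of the following criteria apply". Exclusion 16 sets a limit of at least 2 × ULN on "Aspartate aminotransferase (AST) and alanine aminotransferase (ALT", and after a semicolon a limit above 1.5 × ULN on alkaline phosphatase and bilirubin. In brackets it adds that an isolated bilirubin above 1.5 × ULN "is acceptable if bilirubin is fractionated and direct bilirubin" is below 35%. Section 4.2 allows no deviations from the criteria. Table 2, note 2, makes the screening laboratory results the ones used for the eligibility check.

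**The other numeric limit on transaminases.** Exclusion 19 is "Have a Grade 3 or greater laboratory abnormality based on the protocol toxicity scale", with listed exceptions, none of which concerns transaminases. In Appendix 3, the row "Liver Transferases (AST, ALT, and GGT" puts Grade 2 at above 2.5 to 5.0 × ULN and Grade 3 at above 5.0 to 10.0 × ULN.

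**Liver rules after entry.** Section 5.2.1 stops study treatment "if the following liver chemistry stopping criteria is met", and lists one item: ALT of at least 3 × ULN, with no condition on AST, bilirubin or symptoms. Appendix 1 then says: "Upon completion of the safety follow-up withdraw the subject from the study unless further safety follow up is required". Section 6.2.1 has a different set of criteria: ALT of at least 5 × ULN, or ALT of at least 3 × ULN with raised bilirubin or INR, or with symptoms. It sets out weekly monitoring for subjects with ALT from 3 to below 5 × ULN and bilirubin below 2 × ULN "without hepatitis symptoms or rash, and who can be monitored weekly for 4 weeks".

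**The concern.** The introduction to the list joins the numbered criteria: any one of them excludes. It does not change an *and* inside a criterion into an *or*. Taken at face value, exclusion 16 therefore needs both transaminases to be raised, or both alkaline phosphatase and bilirubin.

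The bilirubin exception points the other way. If bilirubin excluded only together with alkaline phosphatase, an isolated bilirubin rise would never exclude anyone and there would be nothing to exempt. The connector and the exception cannot both be taken literally.

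The protocol's usage elsewhere does not help a site guess. Where either enzyme is enough, it writes *and/or* (Table 1, Table 2 note 4, Sections 6.2.1.1 and 6.2.2). Where two conditions must both hold, as for ALT with bilirubin in Section 6.2.1, it writes *and*. A site that follows this usage would read exclusion 16 as joint. The study is multicentre, so sites could differ. Amendment 01 changed exclusions 7, 10 and 14 and added 21 and 22, but did not touch 16.

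At stake is whether a subject can be dosed with a screening ALT that already satisfies one of the protocol's own liver stopping rules.

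**Working it through.** The plan gives no figure to reproduce on this point. The check is a comparison of thresholds.

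**Inputs** (all in multiples of ULN)
- Exclusion 16: 2 for AST and ALT.
- Exclusion 19 with Appendix 3: excluded if Grade 3 or higher, that is above 5.0.
- Section 5.2.1: ALT ≥ 3.
- Section 6.2.1, criterion 2: ALT ≥ 5.

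**Rules.** The semicolon in exclusion 16 is taken to separate two alternatives; only the transaminase half is evaluated.
- Joint reading: passes if not (AST ≥ 2 and ALT ≥ 2), and neither is above 5.0.
- Single reading: passes if not (AST ≥ 2 or ALT ≥ 2), and neither is above 5.0.

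**Results with AST below 2 × ULN** (AST of 1.0 and of 1.9 give the same pass and stop results)

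| Screening ALT | Grade | Passes, joint | Passes, single | Meets 5.2.1 | Meets 6.2.1 criterion 2 |
|---|---|---|---|---|---|
| 1.9 | 1 | yes | yes | no | no |
| 2.0 | 1 | yes | no | no | no |
| 2.6 | 2 | yes | no | no | no |
| 3.0 | 2 | yes | no | yes | no |
| 4.9 | 2 | yes | no | yes | no |
| 5.0 | 2 | yes | no | yes | yes |
| 5.1 | 3 | no | no | yes | yes |

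On the joint reading, the numerically eligible band that the single reading would close is ALT 2.0 to 5.0 × ULN. The part from 3.0 to 5.0 × ULN meets Section 5.2.1 at entry. By symmetry, isolated AST of 2.0 to 5.0 × ULN with ALT below 2 × ULN also passes, but the stopping criteria do not use AST. On the single reading, the highest eligible ALT is just under 2 × ULN, and no eligible value reaches any liver stopping threshold.

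**Consequences in the analysis.** Treatment is one dose, so after Day 0 there is nothing left to stop. What remains is the Appendix 1 work-up and withdrawal once follow-up is complete. If withdrawal comes before Day 84, late PK samples are lost, and Table 2 shows no PK sample in its discontinuation column. Those samples inform AUC(0-∞), t1/2 and CL, which are primary endpoints. Section 9.2.1 plans 20 subjects to obtain 12 evaluable, a margin of 20 − 12 = 8.

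In the SAP, liver events appear only in listings (Table 5; Listings 26 to 30). ALT of 3.0 to 5.0 × ULN is Grade 2, so a pre-existing elevation could show in Table 2.14, the worst chemistry grade. It would not count by itself in Table 2.18, which needs worsening by at least 2 grades: from Grade 2, that means Grade 4, above 10 × ULN.

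**The case against.** The strongest reply is that exclusion 16 is a compressed list of analytes and limits, and that the bilirubin exception shows that each was meant to count alone. On that reading nothing conflicts, since 2 × ULN lies below 3 × ULN. This is probably the intent. It stands as a reason to correct the wording, but it does not remove the ambiguity in an operative threshold from which deviations are barred.

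Second, exclusions 12 and 13 let the investigator refuse a subject for hepatic disease or laboratory abnormalities. That is true, and no site is obliged to dose such a subject. The safeguard is a judgement without a numeric bound, however, and the Day 0 recheck uses the screening laboratory results.

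Third, a reader might infer that the whole 3 to 5 × ULN band meets the protocol's stopping rules. The documents support this only for Section 5.2.1. Section 6.2.1 provides monitoring for ALT from 3 to below 5 × ULN with bilirubin below 2 × ULN and no symptoms. That disagreement between sections exists whatever exclusion 16 says.

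Fourth, a reader might infer that summaries of liver events would be inflated by pre-existing elevations. The SAP plans no such summary table. It also reports chemistry as change from baseline, and Protocol Section 7.1.2 does not count as adverse events the expected day-to-day fluctuations of pre-existing conditions that do not worsen. Only Table 2.14 and the liver listings are exposed.

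**Conclusion.** The point holds as a drafting inconsistency in an eligibility limit. Read literally, exclusion 16 leaves isolated ALT of 2.0 to 5.0 × ULN numerically eligible, and 3.0 to 5.0 × ULN overlaps Section 5.2.1. A reader might take this to mean that the protocol deliberately admits ALT up to 5 × ULN. The documents do not support that: the 5 × ULN ceiling comes only from exclusion 19, and the bilirubin exception suggests that single limits were intended.

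The practical size is limited. The documents give no frequency of isolated ALT elevation, so the number of affected subjects among about 20 cannot be estimated. Loss of late PK samples is possible rather than certain, because it depends on when follow-up ends. The precision statement in Section 9.2.1 is not shown to be affected. The conclusion assumes the literal connector, AST below 2 × ULN, and no exclusion by judgement under 12 or 13. The correction is still worth making, because the rule governs who is dosed and the change is small.

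**What to change.** Reword exclusion 16 so that it states explicitly, for each of the four analytes, whether its limit applies singly or only jointly, in a form consistent with its own isolated-bilirubin exception. In the same change, reconcile it with Section 5.2.1 and Appendix 1, and with Section 6.2.1, which handles asymptomatic ALT from 3 to below 5 × ULN differently from Section 5.2.1. Which clinical limits apply is for the sponsor to decide; none is proposed here.

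The cost for exclusion 16 is one or two words; aligning the liver sections takes somewhat more text. Both need the ethics review that Section 10.2 requires for amended documents. The sample size and the planned analyses do not change.

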### 4.2.3. Contraception Requirements

#### 4.2.3.1. Female Subjects

Female subjects of childbearing potential must not become pregnant and so must be sexually inactive by abstinence or use contraceptive methods with a failure rate of  $<1\%$ . Female subjects of childbearing potential with same sex partners (when this is their preferred and usual lifestyle) are not required to be abstinent or to use contraception.

#### Abstinence

Sexual inactivity by abstinence must be consistent with the preferred and usual lifestyle of the subject. Periodic abstinence (e.g. calendar, ovulation, symptothermal, post-ovulation methods) and withdrawal are not acceptable methods of contraception.

#### Contraceptive Methods with a Failure Rate of $<1\%$

- Oral contraceptive, either combined or progestogen alone
- Injectable progestogen
- Implants of etonogestrel or levonorgestrel
- Estrogenic vaginal ring
- Percutaneous contraceptive patches
- Intrauterine device (IUD) or intrauterine system (IUS) that meets the  $<1\%$  failure rate as stated in the product label
- **Documented** male partner sterilization prior to **the female subject's entry** into the study, and this male is the sole partner for that subject. For this definition, "documented" refers to the outcome of the investigator's/designee's review of the

subject's medical history for study eligibility, as obtained via a verbal interview with the subject or from the subject's medical records.

- Male condom combined with one of the contraceptive options below:
  - Contraceptive subdermal implant
  - Intrauterine device or intrauterine system
  - Combined estrogen and progestogen oral contraceptive
  - Injectable progestogen
  - Contraceptive vaginal ring Percutaneous contraceptive patches

**NOTE:** These allowed methods of contraception are only effective when used consistently, correctly and in accordance with the product label. The investigator is responsible for ensuring subjects understand how to properly use these methods of contraception.

- MMF and other forms of mycophenolate affect the metabolism of oral contraceptives and may reduce their effectiveness. As such, women receiving mycophenolate who are using oral contraceptives for birth control should employ an additional method (e.g., barrier method).

### **4.3. Withdrawal Criteria and Procedures**

A subject may withdraw from study treatment at any time at his/her own request, or may be withdrawn at any time at the discretion of the investigator for safety, behavioral or administrative reasons.

Should a subject fail to attend the clinic for a required study visit, the site should attempt to contact the subject and re-schedule the missed visit as soon as possible. The site should also counsel the subject on the importance of maintaining the assigned visit schedule and ascertain whether or not the subject wishes to and/or should continue in the study based on previous non-compliance. In cases where the subject does not return for the rescheduled visit or cannot be reached to reschedule the missed visit, the site should make every effort to regain contact with the subject (3 telephone calls and if necessary a certified letter to the subject's last known mailing address) so that they can appropriately be withdrawn from the study.

These contact attempts should be documented in the subject's medical record. Should the subject continue to be unreachable, then and only then will he/she be considered to have withdrawn from the study with a primary reason of "Lost to Follow-up". For all other subjects withdrawing from the study, an alternative reason for discontinuation should be recorded in the Case Report Form (CRF). If a subject prematurely withdraws from participation in the study for any reason, the investigator/sub-investigator must make every effort to assess the items specified on discontinuation test.

Refer to Section 5.2.1 for Liver Chemistry stopping criteria, Section 5.2.2 for QTc withdrawal and Section 7.2 for Pregnancy.

Liver chemistry threshold stopping criteria have been designed to assure subject safety and to evaluate liver event etiology (in alignment with the Food and Drug Administration [FDA] premarketing clinical liver safety guidance). See Section 5.2.1 for details.

#### 4.4. Subject Completion

A subject who participates in all study sessions (including screening, treatment and follow-up) will be considered as having completed the study.

### 5. STUDY TREATMENT

#### 5.1. Investigational Product and Other Study Treatment

	Study Treatment
Product name:	GSK1550188
Formulation description:	GSK1550188 400 mg per vial plus excipients (citric acid/sodium citrate/sucrose/polysorbate)
Dosage form:	Reconstituted solution
Unit dose strength(s)/Dosage level(s):	400 mg per vial (to contain 80 mg/ML when reconstituted with 4.8 ML sterile water for injection [SWFI])
Route/ Administration/ Duration:	Intravenous infusion for over an hour
Physical description:	White uniform lyophilised cake in a 20 ML vial
Manufacturer/ source of procurement:	Human Genome Sciences, Inc.

#### 5.2. Treatment Assignment

Subjects will be assigned to GSK1550188 10 mg/kg treatment in an open label fashion.

##### 5.2.1. Liver Chemistry Stopping Criteria

Liver chemistry threshold stopping criteria have been designed to assure subject safety and to evaluate liver event etiology (in alignment with the FDA premarketing clinical liver safety guidance).

Study treatment will be stopped **for a subject** if the following liver chemistry stopping criteria is met:

- ALT  $\geq 3 \times$ ULN

NOTE: Refer to [Appendix 1](#) for details of the required assessments if a subject meets the above criteria.

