### 6.2.1. Liver Chemistry Follow-up Procedures

**Liver chemistry withdrawal criteria** have been designed to assure subject safety and evaluate liver event etiology.

Liver chemistry stopping criteria 1-3 are defined below:

- 1 ALT  $\geq 3xULN$  **and** bilirubin  $\geq 2xULN$  (>35% direct bilirubin) (or ALT  $\geq 3xULN$  **and** international normalised ratio (INR) >1.5, if INR measure).

NOTE: if serum bilirubin fractionation is not immediately available, study drug should be discontinued if ALT  $\geq 3xULN$  and bilirubin  $\geq 2xULN$ . Serum bilirubin fractionation should be performed if testing is available. If testing is unavailable, **record presence of detectable urinary bilirubin on dipstick**, indicating direct bilirubin elevations and suggesting liver injury.

- 2 ALT  $\geq 5xULN$ .
- 3 ALT  $\geq 3xULN$  if associated with the appearance or worsening of symptoms of hepatitis or hypersensitivity such as fatigue, nausea, vomiting, right upper quadrant pain or tenderness, fever, rash or eosinophilia.

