**In addition, for all subjects with ALT  $\geq 3xULN$ , every attempt must be made to also obtain the following:**

- Viral hepatitis serology including:
  - Hepatitis A IgM antibody.

---

[figure not shown]
 INR testing not required per protocol and the threshold value does not apply to subjects receiving anticoagulants.

- Hepatitis B surface antigen and Hepatitis B Core Antibody (IgM).
- Hepatitis C RNA.
- Cytomegalovirus IgM antibody.
- Epstein-Barr viral capsid antigen IgM antibody (or if unavailable, obtain heterophile antibody or monospot testing).
- Hepatitis E IgM antibody.
- Blood sample for pharmacokinetic (PK) analysis, obtained as per the Time and Events Table (Table 2) of last dose. Record the date/time of the PK blood sample draw and the date/time of the last dose of study treatment prior to blood sample draw on the CRF. If the date or time of the last dose is unclear, provide the subject's best approximation. If the date/time of the last dose cannot be approximated OR a PK sample cannot be collected in the time period indicated above, **do not obtain a PK sample**. Instructions for sample handling and shipping are included in the SPM.
- Serum creatine phosphokinase (CPK) and lactate dehydrogenase (LDH).
- Fractionate bilirubin, if total bilirubin  $\geq 2xULN$ .
- Assess eosinophilia
- Record the appearance or worsening of clinical symptoms of hepatitis (fatigue, nausea, vomiting, right upper quadrant pain or tenderness, fever, rash or eosinophilia) on the AE CRF.
- Record use of concomitant medications, acetaminophen, herbal remedies, other over the counter medications, or putative hepatotoxins on the Concomitant Medications CRF.
- Record alcohol use on the Liver Events CRF.

The following are required for subjects with ALT  $\geq 3xULN$  **and** bilirubin  $\geq 2xULN$  ( $>35\%$  direct) but are optional for other abnormal liver chemistries:

- Anti-nuclear antibody, anti-smooth muscle antibody, and Type 1 anti-liver kidney microsomal antibodies, total IgG.
- Serum acetaminophen adduct high-performance liquid chromatography (HPLC) assay (quantifies potential acetaminophen contribution to liver injury in subjects with definite or likely acetaminophen use in the preceding week).
- Liver imaging (ultrasound, magnetic resonance, or computerized tomography) to evaluate liver disease.
- The Liver Imaging and/or Liver Biopsy CRFs are also to be completed if these tests are performed.

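### Liver stopping rule differs between Protocol 5.2.1/Appendix 1 and 6.2.1/Table 4 for asymptomatic ALT 3 to <5 x ULN (minor); separately, the Discontinuation visit takes no PK or B-cell sample

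*Protocol*

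**What the plan says.** **Liver rule, stricter form.** Protocol 5.2.1 stops treatment "if the following liver chemistry stopping criteria is met" and lists ALT ≥3 x ULN alone, with no bilirubin, INR or symptom condition. The withdrawal section (4.3) points there: "Refer to Section 5.2.1 for Liver Chemistry stopping criteria". Appendix 1 is tied to the 5.2.1 criterion. It requires the liver event CRF. For every subject at or above 3 x ULN it adds a work-up for which "every attempt must be made to also obtain the following". It ends with: "Upon completion of the safety follow-up withdraw the subject from the study unless further safety follow up is required".

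**Liver rule, looser form.** Protocol 6.2.1 uses the same term: "Liver chemistry stopping criteria 1-3 are defined below". Its three criteria are narrower:
- ALT ≥3 x ULN with raised bilirubin or INR;
- ALT ≥5 x ULN;
- ALT ≥3 x ULN with symptoms of hepatitis or hypersensitivity.

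Subjects with ALT 3 to <5 x ULN and bilirubin <2 x ULN, "without hepatitis symptoms or rash, and who can be monitored weekly for 4 weeks", have medical monitor notification and weekly chemistries. For them the text adds: "If at any time these subjects meet the liver chemistry stopping criteria, proceed as described above". The work-up is introduced with "For criteria 1-3, make every attempt to carry out the". Table 4 (7.1.13) waives the liver event CRF in this band unless the elevation lasts 4 weeks or weekly monitoring is not possible.

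**Discontinuation visit.** Protocol Table 2 and its copy in SAP 11.1.1 mark vital signs, concomitant medications, clinical laboratory tests, pregnancy test, ECG and AE review at Discontinuation. The rows for PK sampling and biological markers are blank there. Section 4.3 and footnote 11 of Table 2 ask only for the marked items.

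**The concern.** **Liver rule.** One term carries two definitions. Section 6.2.1 treats a subject in the 3 to <5 x ULN band as not yet having met a stopping criterion, while by 5.2.1 the subject already has. In a multicentre study, the section a site opens decides four things: whether the full work-up is done, whether the liver CRF is completed, whether the subject is later withdrawn or stays to Day 84, and whether the case belongs in SAP Listing 27 (liver stopping events). That listing has no single definition behind it.

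**Discontinuation visit.** This is a separate matter. PK is the primary objective and B-cell subsets are a secondary one, yet a subject who leaves between visits gives neither sample at a visit that already draws blood. Withdrawn subjects are not replaced (SAP 11.5.1). They remain in the PK parameter population whenever parameters can be calculated (Protocol 9.3.1), and neither document states a limit on the extrapolated part of AUC(0-∞). A closing concentration would bear on t1/2, AUC(0-∞), CL and Vz. The first post-dose B-cell sample is on Day 14, so an earlier leaver has no post-dose value.

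**Working it through.** The plan gives no figure for either matter. Its precision figures (Protocol 9.2.1) reproduce but do not depend on this point. With SD = √ln(1+CV²), the half-width at n = 12 is exp(2.201 x SD/√12) − 1. That is 13.4% for CV 20.0% and 22.0% for CV 32.1%, as stated.

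**Step 1: the two liver rules side by side** (INR not varied)

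| ALT (x ULN) | Bilirubin (x ULN) | Symptoms | 5.2.1 | 6.2.1 |
|---|---|---|---|---|
| <3 | any | any | no stop | no stop |
| 3 to <5 | <2 | no | **stop** | **monitor** |
| 3 to <5 | <2 | yes | stop | stop |
| 3 to <5 | ≥2 | any | stop | stop |
| ≥5 | any | any | stop | stop |

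They disagree in one cell only. There, Appendix 1 requires the liver CRF and work-up, which 6.2.1 and Table 4 do not. Both routes have 24-hour notification and weekly chemistries, and 6.2.1.1 adds hepatitis B review above 2.5 x ULN.

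**Step 2: liver-event PK sample.** Section 6.2.1 asks for it 7-14 days after the event, and Appendix 1 asks for it according to Table 2. On nominal days:
- An event at 24 h gives Days 8-15, which includes Day 14.
- An event on Day 14 gives Days 21-28, which includes Days 21 and 28.
- An event on Day 28 gives Days 35-42, which includes Day 42.
- An event on Day 56 gives Days 63-70, and one on Day 84 gives Days 91-98. Neither range contains a Table 2 sample.

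**Step 3: value of a Discontinuation PK sample.** Inputs from Protocol 1.1.2: distribution half-life h1 = 1.1-1.8 days and terminal half-life h2 = 19.4 days at 10 mg/kg. Assumption, not in the documents: a fraction f = 0.30-0.60 of the initial concentration belongs to the distribution phase. The one-hour infusion is treated as instantaneous. The share of AUC(0-∞) lying after day d is

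S(d) = [f·h1·2^(−d/h1) + (1−f)·h2·2^(−d/h2)] / [f·h1 + (1−f)·h2]

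Worked case, f = 0.30 and h1 = 1.1: the denominator is 0.33 + 13.58 = 13.91. S(28) = 13.58 x 0.3677/13.91 = 35.9% and S(35) = 13.58 x 0.2864/13.91 = 28.0%, because the distribution term is negligible by then. A sample at withdrawal on Day 35 therefore gains 7.9 points. Over all four combinations of the range ends:

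| Withdrawal day | Last PK visit | Share without (%) | Share with (%) | Gain (points) |
|---|---|---|---|---|
| 13 | 7 | 69.2-76.1 | 55.2-61.4 | 13.9-14.7 |
| 17.5 | 14 | 53.3-59.2 | 47.0-52.2 | 6.3-7.0 |
| 24.5 | 21 | 41.5-46.1 | 36.6-40.7 | 4.9-5.4 |
| 35 | 28 | 32.3-35.9 | 25.1-28.0 | 7.1-7.9 |
| 41 | 28 | 32.3-35.9 | 20.3-22.6 | 12.0-13.3 |
| 49 | 42 | 19.6-21.8 | 15.2-17.0 | 4.3-4.8 |
| 70 | 56 | 11.9-13.2 | 7.2-8.0 | 4.7-5.2 |

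On a scheduled PK day the gain is zero. For comparison, a completer has 4.4-4.9% left after Day 84.

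**The case against.** **On the liver rule.** The subject has one infusion, and the first scheduled post-dose chemistry is at 24 hours, so no treatment remains to be stopped. Withdrawal under Appendix 1 waits until follow-up is complete, and nothing there cancels scheduled visits meanwhile. Section 4.3 already points to 5.2.1, and a site that follows 5.2.1 and Appendix 1 satisfies both texts. Listing 26 covers monitoring and stopping events together, and no endpoint depends on Listing 27. All of this stands. A reader might infer that the conflict changes dosing, weakens safety cover or costs primary PK data; the documents support none of these. A reader might also take the two liver-event PK instructions as incompatible, but a site can draw at the scheduled visit and again one to two weeks later. The references to a fifth criterion in 6.2.1 and to Phase III-IV in Table 4 are clerical. What survives is that 6.2.1 and Table 4 do not defer to 5.2.1, and a site reading only them would handle this band differently.

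**On the Discontinuation sample.** The protocol and SAP schedules agree, so nothing is contradictory. Liver events already have a PK request, although no B-cell request. Scheduled post-dose ECGs (24 h, Day 84) and pregnancy tests (Days 28, 84) fall at PK times. Some leavers will decline another draw. About 20 are enrolled to secure 12, a margin of eight. The SAP defers to working practices that are not reproduced and may limit extrapolation. These arguments narrow the target to mainly non-liver withdrawals between visits. They do not remove the benefit for those subjects.

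**Conclusion.** There are two separate conclusions, and the figures for the second lend no weight to the first.

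1. The liver text is wrong as written, but the point is minor. The disagreement is confined to asymptomatic ALT 3 to <5 x ULN with bilirubin <2 x ULN. It affects work-up, CRF completion, eventual withdrawal and classification in Listing 27. The documents give no frequency for this band. Exclusion criterion 16 screens AST and ALT at 2 x ULN, so the number is unknown and probably small. That sites would in fact differ is an inference.

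2. The missing Discontinuation samples are a cheap improvement, not an error. The gain is about 4-8 percentage points of extrapolated AUC(0-∞) for withdrawal midway between PK visits from Day 14 on, 14-15 points on Day 13, 12-13 on Day 41, and none on a scheduled PK day. These figures rest on the half-lives in Protocol 1.1.2 and the assumed 30-60% distribution share. They are per withdrawn subject: one subject is 5.0% of 20 enrolled or 8.3% of 12 evaluable (1/20, 1/12). They do not show that the planned precision is at risk.

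**What to change.** **Liver rule.**
- State that 5.2.1 and Appendix 1 govern, and align 6.2.1 and Table 4 with them. Remove the stray fifth criterion and the Phase III-IV label at the same time.
- State whether a subject with asymptomatic ALT 3 to <5 x ULN stays to Day 84.
- Give one liver-event PK window that also works for events found on Day 56 and Day 84.
- Tie SAP Listing 27 to the governing definition.

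**Discontinuation visit.**
- Mark PK sampling and biological markers in the Discontinuation column of Protocol Table 2 and SAP 11.1.1.
- State in the SAP that the PK value enters the non-compartmental calculation at its actual time, consistent with SAP 8.1.3.
- State whether the B-cell value is summarised or only listed, since SAP 11.3.3 keeps unscheduled visits out of summary tables and figures.

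**Cost.** Amendment wording, short SAP statements, and two extra tubes at a visit that already draws blood.
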